#### **6.4.1 Primary Efficacy Endpoint**

ORR is the primary endpoint for all cohorts. Objective response is defined as a CR or a PR on two consecutive tumor assessments  $\geq 4$  weeks apart, as determined by the investigators using RECIST v1.1.

The number of patients included in the analysis and the number of patients with a CR or a PR will be summarized by cohort. The cohort-specified ORR and the corresponding 95% Clopper-Pearson CIs will be calculated.

#### **6.4.2 Secondary Efficacy Endpoints**

OS, defined as the time from enrollment to death from any cause, will be analyzed for all cohorts. The cohort specific results will be summarized as median survival times obtained using Kaplan-Meier methods and their corresponding 95% CIs for median constructed using the Brookmeyer and Crowley method.

PFS, DOR, and DCR will be summarized. PFS is defined as the time from enrollment to the first occurrence of disease progression as determined by the investigator(s) using RECIST v1.1 or to death from any cause, whichever occurs first. DOR is defined as the time from the first occurrence of a documented, confirmed objective response to disease progression as determined by the investigator using RECIST v1.1 or to death from any cause, whichever occurs first. DCR is defined as the proportion of patients with a CR, a PR, or stable disease at 16 weeks as determined by the investigator using RECIST v1.1. For PFS and DOR, cohort-specified median PFS and DOR will be obtained using Kaplan-Meier method, and the corresponding 95% CIs for median will be constructed using the Brookmeyer and Crowley method. Cohort-specified DCR will be summarized as frequency and percentages and the corresponding 95% Clopper-Pearson CIs will be reported.

#### **6.4.3 Exploratory Efficacy Endpoints**

For patients with measurable disease in each cohort, ORR, PFS, DOR, and DCR as determined by the investigator according to immune-modified RECIST will be analyzed using the same methods as described above.

## **6.5 SAFETY ANALYSES**

The safety population will include all enrolled patients who received at least one dose of study drug. The number of patients for safety population will be specified by cohort.

Adverse events, changes in vital signs, changes in laboratory test results, and study treatment exposure will be summarized by cohort.

For each cohort, the occurrence of all adverse events observed during or after the first study drug dose, their severity and verbatim description will be summarized by mapped terms and appropriate thesaurus levels and graded according to NCI CTCAE v4.0. In addition, the incidence and percentages as well as exposure adjusted event rates will be reported for serious adverse events, severe adverse events (Grades  $\geq 3$ ), adverse events of special interest, and adverse events leading to study drug discontinuation or interruption within each cohort. If a patient experiences the same event several times, the occurrence of the event will be counted once at the maximum severity. The causality of all adverse events in relation to the study drug as determined by investigator will also be summarized.

For each cohort, study drug exposure, including treatment duration, number of doses, and dose intensity, will be summarized descriptively.

All deaths and causes of death will be reported as frequency and percentages.

Relevant laboratory data and vital signs will be summarized over time. Abnormal values for laboratory and vital sign data will be identified and summarized.

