#### **4.5.8 Left Ventricular Ejection Fraction**

For patients receiving cobimetinib, evaluations of LVEF are required.

Evaluation of LVEF by ECHO or MUGA scan must be performed at the following timepoints:

- Screening
- Day 1 of Cycle 2 ( $\pm 1$  week)
- At least every 3 months or as clinically indicated
- Treatment discontinuation visit

The treatment discontinuation visit evaluation of LVEF does not need to be performed at the treatment discontinuation visit if an evaluation has been performed within the last 12 weeks and there are no clinically significant findings and/or changes from baseline.

- After restarting treatment with a dose reduction of cobimetinib  
All patients restarting treatment with a dose reduction of cobimetinib because of a decrease in LVEF should have LVEF measurements taken after approximately 2 weeks, 4 weeks, 10 weeks, and 16 weeks, and then resume monitoring of LVEF every three treatment cycles.

Any patient who develops clinical signs or symptoms suspicious of cardiac failure should undergo an LVEF assessment. Evaluation of LVEF must be performed using the same method (ECHO or MUGA scan) for each patient. It is strongly encouraged that the same laboratory and operator perform each ECHO or MUGA scan for each individual patient. Investigators must be aware of local institution regulations regarding repeat MUGA scans.

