#### **5.1.1.1.3 Left Ventricular Dysfunction**

Decreases in LVEF from baseline have been reported in patients receiving cobimetinib. Left ventricular dysfunction may occur with signs and symptoms of cardiac failure, or reduction in LVEF may be asymptomatic.

Left ventricular dysfunction has been characterized in Study GO28141. The study incorporated prospective serial LVEF evaluations in all patients. With active surveillance, measured reductions in LVEF were observed more frequently in patients treated with cobimetinib plus vemurafenib than placebo plus vemurafenib (8.5% vs. 3.7%, respectively, of Grade 2 or 3 decreased LVEF). Of the patients treated with cobimetinib plus vemurafenib, 2 patients (0.8%) had symptomatic reduction in LVEF and the remaining patients were asymptomatic. Most LVEF reduction events in patients treated with cobimetinib plus vemurafenib improved or resolved with management according to dose modification guidelines (see Section 5.1.3).

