a Grade 1: Asymptomatic or mild symptoms; clinical or diagnostic observations only; intervention not indicated.

b Grade 2: Moderate; minimal, local or noninvasive intervention indicated; limiting age appropriate instrumental ADL.

c Grade 3: Severe or medically significant but not immediately sight threatening; hospitalization or prolongation of existing hospitalization indicated; disabling; limiting self-care ADL.

d Grade 4: Sight-threatening consequences; urgent intervention indicated; blindness (20/200 or worse) in the affected eye.

**Table 5 Guidelines for Management of Patients Who Experience Specific Adverse Events (Cobimetinib and Atezolizumab) (cont.)**

Event	Action to Be Taken
Ocular toxicity (cont.)	
Potential immune-related ocular toxicity (e.g., uveitis, iritis, episcleritis, or retinitis)	
 
• Follow guidelines provided in Appendix 8.
 
• Continue cobimetinib as clinically indicated.
 

RVO (any grade)	
 
• If RVO (any grade) is diagnosed, cobimetinib dosing should be permanently discontinued and RVO treated per institutional guidelines.
 
• Continue atezolizumab.
 

RVO = retinal vein occlusion.

**Table 5 Guidelines for Management of Patients Who Experience Specific Adverse Events (Cobimetinib and Atezolizumab) (cont.)**

LVEF Decrease from Baseline				
Patient	LVEF Value	Recommended Action with Cobimetinib and Atezolizumab	LVEF Value following Treatment Break	Recommended Cobimetinib Daily Dose
Asymptomatic	≥ 50% (or 40%–49% and < 10% absolute decrease from baseline)	Continue atezolizumab and cobimetinib at current dose.	NA	NA
	< 40% (or 40%–49% and ≥ 10% absolute decrease from baseline)	Interrupt cobimetinib treatment for 2 weeks. Continue atezolizumab as clinically indicated.	< 10% absolute decrease from baseline	First occurrence: 40 mg
				Second occurrence: 20 mg
				Third occurrence: permanent discontinuation
< 40% (or ≥ 10% absolute decrease from baseline)	Permanent discontinuation			
Symptomatic	NA	Interrupt cobimetinib treatment for 4 weeks. Consider withholding atezolizumab. Discuss with Medical Monitor regarding resumption of atezolizumab. Cardiology consultation is strongly recommended.	Asymptomatic and < 10% absolute decrease from baseline	First occurrence: 40 mg
				Second occurrence: 20 mg

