### **5.2.1 Adverse Events**

According to the ICH guideline for Good Clinical Practice, an adverse event is any untoward medical occurrence in a clinical investigation subject administered a pharmaceutical product, regardless of causal attribution. An adverse event can therefore be any of the following:

- Any unfavorable and unintended sign (including an abnormal laboratory finding), symptom, or disease temporally associated with the use of a medicinal product, whether or not considered related to the medicinal product
- Any new disease or exacerbation of an existing disease (a worsening in the character, frequency, or severity of a known condition), except as described in Section [5.3.5.10](#)
- Recurrence of an intermittent medical condition (e.g., headache) not present at baseline
- Any deterioration in a laboratory value or other clinical test (e.g., ECG, X-ray) that is associated with symptoms or leads to a change in study treatment or concomitant treatment or discontinuation from study drug
- Adverse events that are related to a protocol-mandated intervention, including those that occur prior to assignment of study treatment (e.g., screening invasive procedures such as biopsies)

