### **6.1 DETERMINATION OF SAMPLE SIZE**

The purpose of this study is for hypothesis generation only. No formal hypothesis testing or inference analysis is planned; hence, no power analysis is conducted. Approximately 20 patients are planned to be enrolled in Cohorts 1–6 with possible expansion up to approximately 40 patients in each cohort. Approximately 12 patients are planned to be enrolled in Cohort 7 (biopsy cohort). Therefore, up to approximately 250 patients in total are planned to be enrolled in this study.

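### LVEF is scanned serially but Section 6.5 plans no summary of the measured values, so asymptomatic falls below Grade 3 that change no treatment are reported only if the investigator records them

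*Combined protocol and SAP*

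**What the plan says.** Section 5.1.1.1.3 places left ventricular dysfunction among the important identified risks of cobimetinib: "Decreases in LVEF from baseline have been reported in patients receiving cobimetinib". It adds that a fall may be silent. Section 4.5.8 follows from this: "For patients receiving cobimetinib, evaluations of LVEF are required". Scans are due at screening, at Cycle 2 Day 1, about every three months (every three cycles in Appendix 1, footnote k) and at treatment discontinuation.

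Section 6.5 sets out what is analysed: "Adverse events, changes in vital signs, changes in laboratory test results, and study treatment exposure will be summarized by cohort". It adds deaths, and it restricts its summaries over time and of abnormal values to laboratory and vital-sign data. The safety endpoints in Table 2 are adverse events, vital signs and laboratory results.

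Section 5.2.1 counts deterioration in a clinical test as an adverse event when it is one "that is associated with symptoms or leads to a change in study treatment or concomitant treatment", or when it leads to discontinuation of study drug. For asymptomatic patients with LVEF of 50% or more, or of 40%–49% with an absolute decrease below 10%, Table 5 says: "Continue atezolizumab and cobimetinib at current dose".

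**The concern.** A measurement is mandated because of a known risk, yet no planned analysis uses its values. The only way into the safety results is an adverse event record, and for silent, milder falls the protocol has no rule that makes such a record necessary.

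Three things are at stake. The count of LVEF decreases would be incomplete. It could differ between sites according to recording habit, in a study with about 20 centres, no control arm and cohorts of about 20 to 40. And it could not be set fairly beside the protocol's own reference figure, which rests on measurement: "With active surveillance, measured reductions in LVEF were observed more frequently in patients treated with cobimetinib plus vemurafenib than placebo plus vemurafenib".

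**Working it through.** **1. The plan's own figure.** Section 6.1 gives a maximum of about 250 patients. Six cohorts of 40 plus 12 in Cohort 7 is 6 × 40 + 12 = 252, which reproduces it. The point does not depend on this figure, and there is no power or alpha to check.

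**2. Is LVEF inside any analysed domain?**
- Vital signs (Section 4.5.4): respiratory rate, pulse, blood pressure, temperature. LVEF is not included.
- Laboratory panels (Sections 4.5.6.1 and 4.5.6.2; Appendix 1, footnotes i and j): LVEF is not included.
- Safety endpoints (Table 2): LVEF is not included.
- Exposure and deaths: not relevant.

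Only the adverse event route remains. Laboratory and vital-sign abnormalities that are not adverse events are still tabulated under Section 6.5. LVEF has no such backstop.

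**3. Which falls must become adverse events?**

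| Type of fall | Rule | Captured? |
|---|---|---|
| Symptomatic | Section 5.2.1; symptomatic heart failure is also an event of special interest (5.2.3) | Yes |
| Grade ≥3 reduction, with or without symptoms | Event of special interest (5.2.3) | Yes |
| Asymptomatic, below 40%, or 40%–49% with a decrease ≥10% | Table 5 interrupts cobimetinib, so Section 5.2.1 applies | Yes |
| Asymptomatic, below Grade 3, in the Table 5 row that continues both drugs | No specific rule; only the general clause in 5.2.1 on untoward signs | Investigator's choice |

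**4. How large a fall can stay in the continue row?** Let B be baseline and V the follow-up value, in whole points, reading the absolute decrease as percentage points. Treatment continues if V ≥ 50, whatever the fall, or if V is 40–49 and B − V < 10. For B ≥ 50 the largest fall is therefore the greater of B − 50 and 9:
- B = 55: 9 points
- B = 60: 10 points
- B = 65: 15 points
- B = 70: 20 points
- B = 75: 25 points

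So the row is not confined to small changes. The documents do not give the CTCAE cut-offs for LVEF. Hence they cannot settle which of these falls would reach Grade 3 and be captured as events of special interest.

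**5. How often are measured falls silent?** Section 5.1.1.1.3 reports, for cobimetinib plus vemurafenib in Study GO28141, 8.5% with a Grade 2 or 3 decrease and 2 patients (0.8%) with symptoms. The asymptomatic share is (8.5 − 0.8) / 8.5 = 90.6%. Whole-patient counts consistent with both rounded percentages (for example 21 affected, 19 of them asymptomatic) give 90% to 91%. This shows that symptoms alone would find few cases. It does not show how many asymptomatic cases would escape, because some would have had treatment interrupted or have been Grade 3.

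**The case against.** The strongest reply is that every fall the protocol treats as actionable is already captured, and Section 6.5 reports adverse events by grade, events of special interest, and events leading to interruption or discontinuation. What can escape ends at 50% or above, or at 40%–49% after a fall of less than 10 points. Section 5.1.1.1.3 itself says most events in the earlier study improved or resolved under dose-modification guidance, and events handled by dose modification would be adverse events here. Investigators may also record a silent fall under the general clause of Section 5.2.1, and Section 3.1.2 has the study team review all safety data as it accrues. The study is descriptive: "No formal hypothesis testing or inference analysis is planned; hence, no power analysis is conducted".

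Most of this stands, and it confines the point to the last row of the table above. It does not remove it. Discretionary recording gives neither a complete count nor a uniform one, and ongoing review is monitoring, not a planned analysis. A descriptive study still needs its mandated safety measurements described.

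A reader might infer that the main cardiac harm of cobimetinib would be under-reported. The documents do not support that: symptomatic, Grade ≥3 and treatment-changing falls all reach the report.

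**Conclusion.** The omission is clear from the text. Section 6.5 plans no summary of measured LVEF, and asymptomatic falls below Grade 3 that meet Table 5's continue row are reported only at the investigator's discretion. The rate of measured LVEF decrease would be incomplete, could depend on site, and would not be like-for-like with the 8.5% vs 3.7% benchmark.

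The number of patients affected cannot be derived. A reader might apply the earlier study's asymptomatic rate to the planned total, 250 × (8.5% − 0.8%) = about 19, and take 0 to 19 as the range of missed cases. That product counts asymptomatic Grade 2 or 3 decreases with a different partner drug. It does not count patients in the continue row, and its upper end would require that none had treatment changed, none reached Grade 3 and none was recorded.

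The conclusion assumes that Sections 5.2.1 and 5.2.3 and Table 5 are followed as written. It is a cheap improvement and does not touch the primary endpoint, analysis populations or any decision rule.

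**What to change.** Add to Section 6.5, by cohort, for safety patients with a baseline and at least one post-baseline LVEF, with that denominator stated:
- change from baseline at each scheduled scan, and the worst post-baseline value;
- number and percent by worst NCI CTCAE v4.0 grade derived from the measured values, with the cut-offs written into the plan (without the grade, the table could not be set beside the benchmark);
- number and percent in the LVEF categories Table 5 already uses.

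All of these are counted whether or not an adverse event was recorded.

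Confirm that LVEF values are entered on the eCRF. Appendix 1 exempts gray-shaded assessments from entry, and the shading cannot be seen in the text available. Also reconcile the Appendix 1 grid, which in that text shows no ECHO/MUGA mark at treatment discontinuation, with Section 4.5.8 and footnote k, which call for one unless a recent scan suffices.

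The cost is one extra table, possibly one eCRF field, and a slightly higher reported rate of LVEF decrease. No scan, sample size, dose or management rule changes.

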## **6.6 PHARMACOKINETIC ANALYSES**

The PK analysis population will consist of patients with sufficient data to enable estimation of key parameters, with patients grouped according to treatment received.

PK samples will be collected in this study as outlined in [Appendix 2](#). Cobimetinib and atezolizumab maximum and minimum concentration data ( $C_{max}$  and  $C_{min}$ , respectively) will be tabulated and summarized by study day, as data permit. Summary statistics will include mean, standard deviation, coefficient of variation, median, range, geometric mean, and geometric mean coefficient of variation, as appropriate.

Additional PK and pharmacodynamic analyses will be conducted, as appropriate, based on available data.

## **6.7 IMMUNOGENICITY ANALYSES**

The immunogenicity analyses will include patients with any ADA assessment, with patients grouped according to treatment received.

The number and proportion of ADA-positive patients and ADA-negative patients during both the treatment and follow-up periods will be summarized by treatment group. Patients are considered to be ADA positive if they are ADA negative or missing data at baseline but develop an ADA response following study drug administration (treatment-induced ADA response), or if they are ADA positive at baseline and the titer of one or more post-baseline samples is at least 4-fold greater (i.e.,  $\geq 0.60$ -titer units) than the titer of the baseline sample (treatment-enhanced ADA response). Patients are considered to be ADA negative if they are ADA negative or missing data at baseline, have a post-baseline ADA result, and all post-baseline samples are negative, or if they are ADA positive at baseline but do not have any post-baseline samples with a titer that is at least 4-fold greater than the titer of the baseline sample (treatment unaffected).

The relationship between ADA status and safety, efficacy, PK, and biomarker endpoints may be analyzed and reported descriptively via subgroup analyses.

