**Table 2 Objectives and Corresponding Endpoints (cont.)**

Objective(s)	Corresponding Endpoint(s)
Exploratory Efficacy Objective:	

 
To evaluate the efficacy of cobimetinib plus atezolizumab with immune-modified RECIST
 
	
 
Objective response, defined as a complete response or partial response on two consecutive assessments <math>\geq 4</math> weeks apart, as determined by the investigator according to immune-modified RECIST
 
PFS, defined as the time from enrollment to the first occurrence of disease progression, as determined by the investigator according to immune-modified RECIST, or death from any cause (whichever occurs first)
 
DOR, defined as the time from the first occurrence of a documented objective response to disease progression, as determined by the investigator according to immune-modified RECIST, or death from any cause (whichever occurs first)
 
DCR, defined as the proportion of patients with a complete response, a partial response, or stable disease at 16 weeks, as determined by the investigator according to immune-modified RECIST
 

Safety Objective:	

 
To evaluate the safety of cobimetinib plus atezolizumab
 
	
 
Occurrence and severity of adverse events, with severity determined according to the NCI CTCAE v4.0
 
Change from baseline in targeted vital signs
 
Change from baseline in targeted clinical laboratory test results
 

Pharmacokinetic Objective:	

 
To characterize cobimetinib and atezolizumab pharmacokinetics
 
	
 
Plasma concentration of cobimetinib at specified timepoints
 
Serum concentration of atezolizumab at specified timepoints
 

Immunogenicity Objective:	

 
To evaluate the immune response to atezolizumab
 
	
 
Presence of ADAs during the study relative to the presence of ADAs at baseline
 

ADA=anti-drug antibody; DCR=disease control rate; DOR=duration of response; NCI CTCAE v4.0=National Cancer Institute Common Terminology Criteria for Adverse Events, Version 4.0; PFS=progression-free survival; RECIST=Response Evaluation Criteria in Solid Tumors.

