#### **Inclusion Criteria for UC Cohort 5 (Progression while on Anti-PD-1/PD-L1 Therapy):**

- Patients in UC Cohort 5 must meet the following criteria for study entry:
- Histologically or cytologically documented locally advanced (T4b, any N; or any T, N2–N3) or metastatic (M1, Stage IV) urothelial bladder cancer (also termed transitional cell carcinoma, urothelial carcinoma, or carcinoma of the urinary tract; including renal pelvis, ureters, urinary bladder, and urethra)

Patients with mixed histologies are required to have a dominant transitional cell pattern.

- Locally advanced bladder cancer must be inoperable on the basis of involvement of pelvic sidewall or adjacent viscera (clinical stage T4b) or bulky nodal metastasis (N2–N3)

Transurethral resection for bladder tumor (TURBT) specimens must contain a muscle-invasive component (i.e., T2 or greater) or the bladder tumor as verified by local pathology review. If the TURBT specimens do not contain a muscle-invasive component, then specimens obtained at the time of cystectomy, nephroureterectomy, or metastatic spread (i.e., a sample from a metastatic lesion) will be required prior to enrollment.

- Disease progression during or following treatment with at least one platinum-containing regimen for inoperable, locally advanced or metastatic urothelial bladder cancer or disease recurrence
  - Patients who received prior adjuvant/neoadjuvant chemotherapy and progressed within 12 months of treatment with a platinum-containing adjuvant or neoadjuvant regimen are eligible.
  - Patients who have received one cycle of a platinum-containing regimen but discontinued because intolerable toxicity may also be eligible.
  - Patients with disease progression following chemoradiotherapy must demonstrate progression outside the prior radiotherapy port.
- Progression while on a prior anti-PD-1/PD-L1 therapy in the recurrent or metastatic setting
  - Patients are also eligible if they had disease progression on or within 6 months of the last dose of anti-PD-1/PD-L1 therapy in the adjuvant setting
- Prior treatment with T-cell co-stimulating or immune checkpoint blockade therapies, and combinations including anti-CTLA-4, anti-PD-1/PD-L1 therapeutic antibodies are allowed
- Patients are eligible if they received no more than three lines of therapy in the advanced, metastatic setting

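### Section 6.7 lets patients with only a baseline ADA sample into the incidence denominator, and its ADA-negative rule for baseline-positive patients omits the post-baseline result it demands of the others

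*Combined protocol and SAP*

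**What the plan says.** The immunogenicity endpoint in Table 2 is "Presence of ADAs during the study relative to the presence of ADAs at baseline". Section 6.7 sets the analysis population, "The immunogenicity analyses will include patients with any ADA assessment", and the reported quantity: "The number and proportion of ADA-positive patients and ADA-negative patients during both the treatment and follow-up periods will be summarized by treatment group". It gives no separate denominator for those proportions.

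Section 6.7 then classifies patients.

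- **ADA positive:** patients who are "ADA negative or missing data at baseline but develop an ADA response following study drug administration" (treatment-induced), or who are positive at baseline and later show at least a 4-fold rise in titer (treatment-enhanced).
- **ADA negative, branch 1:** patients negative or missing at baseline who "have a post-baseline ADA result, and all post-baseline samples are negative".
- **ADA negative, branch 2:** patients "ADA positive at baseline but do not have any post-baseline samples with a titer that is at least 4-fold greater" than at baseline (treatment unaffected).

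The relationship of ADA status to safety, efficacy, PK and biomarkers may be examined descriptively in subgroups. Appendix 2 schedules the ADA samples.

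**The concern.** Treatment-emergent ADA incidence can be observed only in patients sampled after dosing. The population sentence also admits patients sampled only before dosing. If they stay in the denominator, the ADA-positive proportion is diluted.

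The two ADA-negative branches are also asymmetric: branch 1 guards against a missing follow-up result and branch 2 does not. Under branch 2, absence of data is recorded as absence of a titer rise. The reported incidence is at stake, together with the make-up of the ADA-negative group in any ADA subgroup display. Cohorts are small (about 20, up to about 40; about 12 in Cohort 7, Section 6.1), so one to three patients move a cohort-level percentage visibly.

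**Working it through.** **No figure to reproduce.** The documents state no expected ADA rate and no share of patients without a post-baseline sample. The one numerical rule in Section 6.7 is consistent: log10(4) = 0.602, in line with the stated 0.60 titer units.

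**Step 1: can a patient have only a baseline sample?** Appendix 2 takes the first ADA sample before the first atezolizumab infusion: Cycle 1 Day 1 in Cohorts 1–6, Cycle 1 Day 15 in Cohort 7. The post-infusion sample at that visit is for PK only. The next scheduled on-treatment ADA sample is Cycle 2 Day 1, which is Day 29 (28-day cycle), or 29 − 15 = 14 days after the first infusion in Cohort 7. ADA samples are also scheduled at atezolizumab discontinuation and more than 90 days after the last infusion. Baseline-only patients are therefore those who leave before Day 29 and miss both later visits.

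**Step 2: the rules applied case by case.**

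| Baseline | Post-baseline samples | In the analysis set? | Class under Section 6.7 |
|---|---|---|---|
| Negative | None | Yes | Neither |
| Positive | None | Yes | ADA negative, read literally |
| Missing | None | No (no assessment at all) | Neither |
| Negative or missing | All negative | Yes | ADA negative |
| Positive | Some, none 4-fold higher | Yes | ADA negative |
| Negative or missing | At least one positive | Yes | ADA positive, treatment-induced |

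The first two rows are the problem.

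**Step 3: denominator effect.** Let p be incidence among patients with a post-baseline result and m the share of the set with a baseline sample only. The reported proportion is p(1 − m). The effect depends on the share m, so pooling cohorts does not remove it. Assumed illustration, 20 patients with 4 positives:

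- 1 baseline-only (m = 5%): 4/19 = 21.1%, reported as 4/20 = 20.0%
- 2 baseline-only (m = 10%): 4/18 = 22.2%, reported as 20.0%
- 3 baseline-only (m = 15%): 4/17 = 23.5%, reported as 20.0%

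The understatement is 1.1 to 3.5 percentage points.

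**Step 4: effect of branch 2.** Take the case with 3 baseline-only patients, so that 17 − 4 = 13 patients are negative on actual post-baseline data.

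- All 3 baseline negative: 4/20 = 20% positive, 13/20 = 65% negative, 3/20 = 15% unclassified.
- 1 of the 3 baseline positive: negatives become 14/20 = 70%, the extra one with no follow-up sample.
- With a post-baseline result required throughout: 4/17 = 23.5% positive, 13/17 = 76.5% negative.

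Suppose instead that the denominator is read as classified patients only. Branch 2 still matters: with 1 baseline-positive patient among the 3, the rate is 4/(4 + 14) = 22.2%, not 23.5%.

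**The case against.** **The denominator is inferred.** Section 6.7 says who is included; it does not say what the proportions are divided by. Baseline samples have a legitimate use because the endpoint is relative to baseline, and dividing by classified patients is a fair reading. This stands as a caution. But the population sentence is the only denominator the text offers, and the alternative reading does not close the branch 2 gap (step 4).

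**Few patients may be affected.** The discontinuation and >90-day samples are aimed at patients who stop early, so they reduce the baseline-only share. This also stands: 5% to 15% is an assumption. Even if it is granted, a shift of 1.1 to 3.5 points is small against the exact 95% interval for 4/20, 5.7% to 43.7%, in a study described as hypothesis-generating.

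**Stronger readings that the documents do not support.**

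- A reader might infer that early drop-outs in general are placed among the ADA negatives and so distort ADA-by-efficacy comparisons. Branch 1 prevents this for patients negative or missing at baseline; only baseline-positive patients slip through. The subgroup comparisons are optional and descriptive.
- A reader might infer that treating a missing baseline like a negative one is an outright error in the pretreated cohorts. The UC Cohort 5 criteria do state that prior anti-PD-1/PD-L1 "therapeutic antibodies are allowed", and nothing bars prior atezolizumab in Cohorts 4–7. But misclassification needs a missed baseline sample, pre-existing antibodies that the atezolizumab assay detects (Section 4.5.6.3), and their persistence after baseline. The documents give no numbers for this. The rule is prespecified and errs toward reporting more immunogenicity.

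**Conclusion.** The point holds as a minor defect in the stated rules. Followed literally, Section 6.7 admits baseline-only patients to the only denominator it offers and classes a baseline-positive patient with no follow-up sample as ADA negative. On the assumed inputs (20 patients, 4 positives, 1 to 3 baseline-only), 20.0% is reported where 21.1% to 23.5% applies. The actual baseline-only share is not in the documents.

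It would go too far to conclude that the published incidence will be biased in a known direction. The denominator effect lowers it; counting missing baselines as negative can raise it. Neither size is given, so the net effect is undetermined. The consequences stop at the descriptive immunogenicity endpoint and the optional ADA subgroups. ORR is unaffected.

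**What to change.** Amend the wording of Section 6.7:

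1. Define the ADA-evaluable set for incidence as patients with at least one post-baseline ADA result, and name it as the denominator for the ADA-positive and ADA-negative proportions.
2. Require a post-baseline ADA result in both ADA-negative branches.
3. Report baseline ADA prevalence on its own denominator, patients with a baseline result. Baseline-only patients then still contribute where they are informative.
4. Optionally, as a secondary display, list patients with a missing baseline and a later positive separately in Cohorts 4–7, where prior atezolizumab is possible.

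The cost is a text change and the matching table specifications. There are no new samples, no additional visits and no change to patient care.
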